	
2. VAS3. How many oxycodone or other narcotic medications are you taking post-op4. Are you able to return to work?5. Are you satisfied with the procedure, and would you choose to have it again for a similar problem? 
- Take the ADL questionnaire (see next section)- If in person (part of standard care, only collected by study staff, measurements performed by caregivers): Perform the following measurements: range of motion of the PIP joint of the affected finger (including noting any flexion contracture), distance fingertip to distal palmar crease (DPC), and grip strength using Jamar 2 setting.-
Visit/Telephone call 7 (6 months +- 1 week after surgery)	
- Take the following questionnaire:- 1. Are you able to return to activities of daily living, and what activities do you still have trouble doing? You can list the activities you are having trouble with.2. VAS3. How many oxycodone or other narcotic medications are you taking post-op4. Are you able to return to work?5. Are you satisfied with the procedure, and would you choose to have it again for a similar problem? 
- Take the ADL questionnaire (see next section)- If in person (part of standard care, only collected by study staff, measurements performed by caregivers): Perform the following measurements: range of motion of the PIP joint of the affected finger (including noting any flexion contracture), distance fingertip to distal palmar crease (DPC), and grip strength using Jamar 2 setting.

We will call or e-mail patients to ask them to complete questionnaires (see above) through Redcap.

Procedures

The intervention groups consist of:

- Open trigger finger release
 - o The A1 pulley is reached through a transverse incision under local anesthesia and monitored anesthesia care. It is then divided longitudinally. The patient is asked to flex and extend the affected finger. If triggering has been resolved, the wound is closed with sutures (12).
- Ultrasound-guided trigger finger release
 - o The A1 pulley is identified with the use of ultrasound. The pulley is released with a trigger finger device under local anesthesia and monitored anesthesia care (9).

Specific data variables to be collected

The variables that will be collected are:

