We will use a student t-test to analyze normally distributed continuous data. When we compare data at two different time points within a group, we will use a paired student t-test. When we compare continuous data of two different groups, we will use an unpaired student t-test.

We will use a Mann-Whitney U test if the continuous data is not normally distributed.

We will use Fischer's exact test or a Chi-squared test for differences in categorical variables, depending on the number of events in the different groups.

Power analysis

We have performed a power analysis to find differences between two independent means (normally distributed) with alpha = 0.05, power = 0.80, and effect size 0.5. This would require a total sample size of 102 patients (51 in each group). If the data is non-normally distributed with the same alpha, power, and effect size, we would need a total of 106 patients (53 in each group).

This power analysis is performed for our most important primary outcomes: the 5-question and ADL questionnaires.

5. Monitoring and Quality Assurance

The full-time research coordinator and principal investigator are responsible for adherence to all IRB policies and guidelines and for the accuracy and completeness of all forms, entries, and informed consent.

Study data will be maintained in a locked filing cabinet and/or on password-protected computers. Questionnaires and self-reported responses will not become part of the subject's medical record. Hard copies of study-related data and forms will be stored in a lockable file cabinet. Only the investigators and study staff will have access to this information. Any magnetic or electronic information will be saved in password-protected computers, which only study staff members can access. REDCap, secure and HIPAA-compliant, will be used to collect all answers.

For guidance, refer to the following Partners policies:

Data and Safety Monitoring Plans and Quality Assurance

https://partnershealthcare-public.sharepoint.com/ClinicalResearch/DSMP_in_Human_Subjects_Research.pdf

Reporting Unanticipated Problems (including Adverse Events)

https://partnershealthcare-public.sharepoint.com/ClinicalResearch/Reporting_Unanticipated_Problems_including_Adverse_Events.pdf

6. Privacy and Confidentiality

- Study procedures will be conducted in a private setting
- Only data and/or specimens necessary for the conduct of the study will be collected

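### VAS and ADL are collected at six postoperative contacts but compared between arms only by two-sample tests, which can mislead if recovery-related non-reply differs by arm

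*Combined protocol and SAP*

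**What the plan says.** All references are to the combined protocol and SAP.

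- **Schedule (6. Study Procedures, visit table).** VAS and the ADL questionnaire are taken at visit 1, before surgery, and at contacts 2 to 7, from days 2-4 to 6 months.
- **Collection.** "We will call or e-mail patients to ask them to complete questionnaires (see above) through Redcap". The section on site-specific procedures adds that visits in the first 3 months are routine care. At 6 months, patients with persistent problems are seen, and those doing well are only phoned or e-mailed. The telephone script allows a patient to decline.
- **Endpoints.** The five questions (including VAS) and the ADL questionnaire are primary, and the power analysis calls them the most important. No primary time point is named, and the fifteen ADL items have no scoring rule.
- **Between-arm tests (4. Statistical Analysis).** The parametric comparison is given as: "When we compare continuous data of two different groups, we will use an unpaired student t-test". A rank test is the fallback when normality fails: "We will use a Mann-Whitney U test if the continuous data is not normally distributed". Categorical items get Fisher's exact or chi-squared tests.
- **Within-arm test.** "When we compare data at two different time points within a group, we will use a paired student t-test". This does not compare the arms.
- **Not stated.** There is no repeated-measures model, summary over time, analysis set, missing-data rule or allowance for non-reply.
- **Baseline and allocation (5. Subject Enrollment).** Patients without a preoperative questionnaire are withdrawn, so every retained patient should have a baseline value. Arm is set by the treating surgeon.

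**The concern.** A two-sample test needs one number per patient. With no summary over time defined, that number is naturally the answer at one contact, and a patient who did not reply there drops out of the comparison. The answers that would show how that patient was doing just before, and at baseline, go unused.

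If better-recovered patients skip more often in one arm, the repliers in that arm look worse than the arm really is. In a non-randomised comparison of two techniques, that gap would be read as an effect of technique. The data needed to reduce the problem are already being collected.

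**Working it through.** **1. The plan's own figure.** Inputs: "with alpha = 0.05, power = 0.80, and effect size 0.5", equal groups. The exact one-sided two-sample t calculation gives 50.15 per arm, so 51 per arm and 102 in total. Dividing by the Mann-Whitney efficiency, 50.15/0.955 = 52.5, so 53 per arm and 106 in total. Both stated sizes reproduce, but only as one-sided calculations; a two-sided test needs 64 per arm (128). Neither size includes an allowance for non-reply. The planned effect of 0.5 SD is the yardstick below.

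**2. Size of the bias, by formula.** Assumptions, not in the documents: standard normal scores with lower meaning better, no true arm difference, correlation 0.6 between any two contacts, and 10% base non-reply. In one arm only, patients better than average skip 40% or 50% of the time.

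The halves of a standard normal below and above zero have means -0.798 and +0.798. With reply probability rL in the better half and rH in the worse half, repliers have mean 0.798 × (rH - rL)/(rH + rL).

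- 40% skipping: 0.798 × (0.90 - 0.60)/(0.90 + 0.60) = 0.160 SD.
- 50% skipping: 0.798 × (0.90 - 0.50)/(0.90 + 0.50) = 0.228 SD.

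These apply when the current, unrecorded score drives skipping. If the preceding recorded score drives it, multiply by the correlation: 0.6 × 0.160 = 0.096 SD and 0.6 × 0.228 = 0.137 SD. The other arm's repliers have mean 0, so these are also the arm differences. If both arms follow the same rule, the two means cancel.

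The multiplied values are exact at the first postoperative contact. Simulation with 60,000 patients per arm gave 0.095-0.105 and 0.131-0.141 SD over all six contacts, with reply rates of 73% and 67% against 90%. Relative to 0.5 SD, 0.10 and 0.14 are 20% and 28%.

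**3. Effect on the test at 51 per arm.** Repliers are 51 × 0.73 = 37.2 or 51 × 0.67 = 34.2 in one arm and 51 × 0.90 = 45.9 in the other. The standard errors are √(1/37.2 + 1/45.9) = 0.221 and √(1/34.2 + 1/45.9) = 0.226. The shifts are 0.096/0.221 = 0.43 and 0.137/0.226 = 0.61 standard errors. A nominal two-sided 5% test then rejects about 7% and 9% of the time.

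**4. What a longitudinal model recovers, same settings.** When the last recorded score drove skipping, likelihood estimation on all contacts left a difference within 0.012 SD of zero. When the current unrecorded score drove it, about 0.08 of 0.16 SD and 0.11 of 0.23 SD remained, roughly half.

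**5. A wider set of patterns.** This used 1,000 simulated trials per scenario with 51 per arm and no true difference. Correlation was 0.5 or 0.7 (equal), or 0.7 decaying with lag. Non-reply had a logit slope of 1 per SD, and 22% to 33% were missing at 6 months. The 6-month t-test was compared with a repeated-measures model with unstructured covariance, arm by time and baseline by time.

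| Driver of non-reply | Link with score | t-test bias (SD); false positives | Model bias (SD); false positives |
|---|---|---|---|
| Previous recorded score | same in both arms | 0.01 or less; 3-4% | 0.01 or less; 4-5% |
| Previous recorded score | one arm only | 0.12-0.20; 7-14% | 0.00; 4-5% |
| Previous recorded score | opposite in the two arms | 0.23-0.39; 15-42% | 0.00; 4-5% |
| Current score, single misses | same in both arms | 0.00; 5-6% | 0.01 or less; 6-7% |
| Current score, single misses | one arm only | 0.21-0.22; 16-17% | 0.08-0.15; 9-11% |
| Current score, dropout | opposite in the two arms | 0.33-0.47; 28-54% | 0.10-0.18; 11-14% |

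The opposite-link rows are extremes and mark the outer edge of the range.

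**The case against.** The strongest reply is that nothing in the documents shows the condition on which the bias depends. Both arms share one schedule, one e-mail script, one telephone script and one 6-month contact rule. Nothing makes questionnaire follow-up specific to a surgeon. In the one-arm scenario of steps 2 and 3 the false-positive rate rises only to about 7-9%. All of this stands. It limits the point to an exposure and does not show that bias will occur.

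Five stronger readings are tempting and are not supported:

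- **That the plan prescribes testing each contact on repliers only.** It names families of tests and is silent on time point and analysis set. One contact at a time is the default reading of those tests, not the plan's text.
- **That any recovery-related non-reply biases the comparison.** With no true difference, an identical pattern in both arms gives a bias of about zero.
- **That follow-up practice differs between arms.** Surgeon-determined allocation makes this possible; no section states it.
- **That answers come mostly by remote reply.** Remote collection is described, but five of the six postoperative contacts fall within the period of routine visits, and the split is not given.
- **That a mixed model would remove the problem.** It does so only when recorded answers explain non-reply.

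The objection does not answer the choice of method. The plan names tests that discard the baseline value and all but one answer per patient, and a better analysis of the same data is available.

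**Conclusion.** The point holds as a conditional weakness of the stated between-arm method and should be corrected. If the link between recovery and non-reply differs by arm, the planned tests can show a false difference of about 0.10-0.14 SD under one-arm skipping of 40-50% among better patients. It can be larger under stronger or opposite patterns, and is about zero if the pattern is the same in both arms.

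The missingness patterns, the correlations and the normal scores are assumptions; the documents give no reply rates. A mixed model removes the bias when recorded answers explain non-reply. It left about half under the same settings when the current score was the driver, so a sensitivity analysis belongs with it. Confounding by surgeon is a separate problem that this model does not address.

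**What to change.** In 4. Statistical Analysis, before the arms are compared:

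1. Define the ADL score (total or mean of the fifteen items, with a rule for missing items) and name the contact or contacts to be analysed.
2. For VAS and the ADL score, make the main between-arm analysis one linear mixed model per outcome over the six postoperative contacts. Include arm, contact, arm by contact, the preoperative value and its interaction with contact. Use unstructured covariance and all answered contacts. Report the arm difference, with its confidence interval, at the named contact(s).
3. For the yes/no items, use a mixed logistic model or weighted GEE. Ordinary GEE is not protected when data are missing at random.
4. Keep the t-test and Mann-Whitney as supportive analyses.
5. Add a missing-not-at-random sensitivity analysis, for example shifting the unrecorded scores by a range of amounts separately in each arm. Report reply rates by arm and contact.
6. Give return-to-work time, pill counts and recurrence their own methods.

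The cost is analysis wording and a little programming, with no new data. The main analysis would rely on data being missing at random given the recorded answers, which is why item 5 is needed. The unstructured covariance for six contacts has 6 × 7/2 = 21 parameters, so a fallback structure should be named in case the model does not converge at about 102 patients.

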3. General Description of Study Design

Retrospective part

Patient characteristics and disease-related (trigger finger) variables will be collected retrospectively from patient charts on EPIC.

Prospective part

This will be a prospective two-arm study. Patients will either be treated with ultrasound-guided trigger finger release or open trigger finger release (conventional method). [name] is the only surgeon within the Mass General Brigham (MGB) hospitals that performs ultrasound-guided trigger finger release. All other surgeons perform open trigger finger releases.

Surgeons will measure range of motion and grip strength preoperatively and during postoperative visits, which is part of routine care. We will also administer questionnaires to see how patients are doing postoperatively. See the '6. Study Procedures' for a more elaborate description of the visits.

4. Subject Selection

Inclusion criteria:

1. ≥ 18 years of age
2. Clinical diagnosis of trigger finger
3. Patient has failed conservative treatment or elects not to undergo conservative treatment
4. Surgeon agrees that surgery is indicated
5. Subject agrees to complete follow-up questionnaires over a 6-month period

Exclusion criteria:

1. Prior surgery on the target finger
2. History of prior surgical pulley release in the target hand
3. History of prior surgical pulley release in the contralateral hand within 3 months of enrollment or with persistent symptoms that interfere with normal daily activities or work at the time of consent
4. Corticosteroid injection in the target finger or hand within 6 weeks of surgery
5. Presence of additional process in the target wrist or hand requiring additional intervention beyond pulley release (e.g., neurolysis, mass removal, tenosynovectomy)
6. Clinically significant trauma or deformity of the upper limb (shoulder to hand) on the target side
7. Clinically significant vascular disease (including Raynaud's phenomenon) of the upper limb (shoulder to hand) on the target side
8. Clinically significant neurological disorder (including complex regional pain syndrome) of the upper limb (shoulder to hand) on the target side
9. Planned surgical or interventional procedure on the contralateral wrist or hand

10. Systemic inflammatory disease (e.g., rheumatoid arthritis, lupus)
11. Amyloidosis
12. Diabetes not controlled by a stable dose of medication over the past three months
13. Pregnant or planning pregnancy in the next 6 months
14. Workers' compensation subjects

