We will include all patients who meet the inclusion criteria. We do not exclude patients based on race, color, national origin, sex, sexual orientation, or religion. We will not enroll vulnerable patient populations in this study.

5. Subject Enrollment

Patients will be prescreened through retrospective manual chart review.

Patients will be contacted in person at one of the MGB hospitals (MGH main campus, MGH Waltham, MGH Danvers, BWH main campus, BWH Faulkner, and BWH Foxborough). Patients who meet the inclusion criteria will get a summary of the study by an orthopedic surgeon or a study staff member to see if they are interested. If patients are interested, they will receive the study fact sheet, and the surgeon or study staff member will explain the study in more detail and answer any questions the patient may have. Subjects will be asked to complete the questionnaire either in person or over email or telephone before surgery. Subjects who opt to not complete the questionnaire in person will be contacted using the email or telephone script approved in this study. Subjects who do not complete the pre-op questionnaire before surgery will be withdrawn. Subjects can opt to receive an encrypted or unencrypted email. Subjects who indicate verbally in the outpatient clinic that they do not wish to participate will not be included in the study.

Depending on the treating surgeon, patients will either be treated with an open trigger finger release or an ultrasound-guided trigger finger release.

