- Range of motion of the PIP joint of the affected finger using a goniometer (in degrees), including any flexion contracture + Distance of fingertip from DPC
- Grip strength in the affected as well as contralateral hand using a dynamometer at Jamar 3 setting (in lbs)
- Return to activities of daily living. One question is: 'What activities can't you do?'. We also take a questionnaire to rate their ability to do certain activities (see questionnaire under this section). Patients can rate their ability to perform each activity on a scale from 1 to 5 (1 indicating no difficulty and 5 indicating unable to perform).
- VAS (a pain scale from 1 – 10, reported by the patient)
- How many oxycodone or other narcotic medications are you taking post-op? The number of pills taken will be given.
- Return to work. Patients give a date of when they started working again. Then we'll calculate the return to work in weeks
- Are you satisfied with the procedure, and would you choose to have it again for a similar problem? Answered with yes or no.
- Complications (i.e., trigger finger recurrence, infection, bleeding, etc.)

ADL questionnaire

Mass General Brigham Institutional Review Board
Intervention/Interaction Detailed Protocol

Opening jar	1	2	3	4	5
Driving	1	2	3	4	5
Household Chores	1	2	3	4	5
Carrying Groceries	1	2	3	4	5
Buttoning	1	2	3	4	5
Bathing	1	2	3	4	5
Cooking	1	2	3	4	5
Writing	1	2	3	4	5
Dressing	1	2	3	4	5
Shopping	1	2	3	4	5
Holding a book	1	2	3	4	5
Eating	1	2	3	4	5
Using a Computer	1	2	3	4	5
Holding a Phone	1	2	3	4	5
Using Toilet	1	2	3	4	5

Description of plans for return of research results as applicable

Not applicable

Definition of primary and secondary outcomes/endpoints

Primary endpoints:

- The 5 questions asked in the section above, together with the *ADL questionnaire*
- Recurrence of trigger finger or incomplete release

Secondary endpoints:

- Range of motion of the PIP joint of the affected finger (including noting any flexion contracture)
- Distance fingertip to distal palmar crease
- Grip strength in the affected hand
- Other complications than recurrence of trigger finger or incomplete release

Local site restrictions or site-specific procedures as applicable

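### Return to work, measured in weeks from a reported date, has no rule for patients without a date; a lesser gap is that no paired test is named for non-normal data

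*Combined protocol and SAP*

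**What the plan says.** **Return to work.** Under Definition of primary and secondary outcomes/endpoints, the first primary endpoint is "The 5 questions asked in the section above, together with the" ADL questionnaire. Return to work is one of those five questions. Under Specific data variables to be collected, "Patients give a date of when they started working again", and the team will then "calculate the return to work in weeks". The Study visits table asks about ability to work at each of the six postoperative contacts, but Visit 1 has no work question. Subject Selection excludes workers' compensation patients and does not require employment. The Benefits section names faster return to work as a possible advantage of the ultrasound-guided technique.

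**Tests.** The Statistical Analysis section gives the unpaired t-test for two groups. For one group over time it says: "When we compare data at two different time points within a group, we will use a paired student t-test". For non-normal data the only instruction is "We will use a Mann-Whitney U test if the continuous data is not normally distributed". Fisher's exact or Chi-squared tests cover categorical variables. The section contains no time-to-event method, censoring rule, missing-data rule or paired rank test.

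**Before-after data will exist.** VAS and ADL are taken at Visit 1. Subject Enrollment states "Subjects who do not complete the pre-op questionnaire before surgery will be withdrawn", and General Description of Study Design states "Surgeons will measure range of motion and grip strength preoperatively and during postoperative visits".

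**The concern.** A patient who has not returned by 6 months, or who is lost before returning, has no number of weeks. A t-test or Mann-Whitney test on weeks can only leave that patient out. Late returners are the most likely to be undated, so the remaining times are too short. How much too short can differ between arms, because it depends on each arm's return times, spread and loss. The choice between dropping, ranking and censoring these patients also stays open until the data are seen, in an unrandomised study and on a primary question.

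The second gap is smaller. The plan foresees within-group comparisons, but its one test for non-normal data assumes independent samples. Read literally, paired data would be tested as unpaired. Read as the counterpart of the unpaired t-test only, the paired case has no test. What is at stake is sensitivity to modest before-after changes.

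**Working it through.** **Sample size used.** The plan says "we would need a total of 106 patients (53 in each group") for non-normal data. This figure reproduces as a one-sided calculation: 50.15 per group for a t-test at effect size 0.5, alpha 0.05 and power 0.80, divided by the Mann-Whitney efficiency 3/π, gives 52.5, so 53. The plan does not state sidedness; that is a separate matter. Below, n = 53 per group and tests are two-sided at 5%.

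**Return to work: assumptions.** The documents give no return times, spread or loss. I assume log-normal times with median M days and log-scale SD σ, follow-up of 182 days, and a share p lost at a time uniform over follow-up and unrelated to return.

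*No loss, by hand.* The median m among dated patients solves Φ(ln(m/M)/σ) = ½·Φ(ln(182/M)/σ). With σ = 1.3:
- M = 42: ln(182/42)/1.3 = 1.128; Φ = 0.870; half is 0.435, so z = −0.163 and m = 42·exp(−0.212) = 34.0.
- M = 21: ln(182/21)/1.3 = 1.661; Φ = 0.952; half is 0.476, so z = −0.061 and m = 21·exp(−0.079) = 19.4.
- Ratio 34.0/19.4 = 1.75 against a true 2.0.

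*With loss.* A return on day t is seen with probability 1 − p·t/182, so dated times have density proportional to f(t)·(1 − p·t/182). Numerical integration gives:

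| Assumed case (slow arm / fast arm) | Undated | Medians among dated | Ratio | True |
|---|---|---|---|---|
| 14/7 days, σ 1.0, 20% loss | 2.9% / 1.3% | 13.6 / 6.9 | 1.97 | 2.0 |
| 42/21 days, σ 1.0, 20% loss | 12.3% / 4.9% | 36.9 / 20.0 | 1.84 | 2.0 |
| 42/21 days, σ 1.3, 20% loss | 17.6% / 8.3% | 32.2 / 18.6 | 1.73 | 2.0 |
| 42/21 days, σ 0.6 / 1.3, 20% loss | 6.1% / 8.3% | 41.0 / 18.6 | 2.20 | 2.0 |
| 42/21 days, σ 1.3 / 0.6, 20% loss | 17.6% / 2.8% | 32.2 / 20.8 | 1.55 | 2.0 |
| 30/30 days, σ 1.3, 10% / 40% loss | 10.3% / 16.5% | 25.6 / 23.7 | 1.08 | 1.0 |

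In the last case the simulated type I error of Mann-Whitney on dated patients is about 6%.

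*Rejection rates of the alternatives* (5,000 simulated trials per case):

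| Case | Dated only, Mann-Whitney | Non-returners ranked last | Log-rank | Peto-Prentice |
|---|---|---|---|---|
| 42/21, σ 1.3, 20% loss | 56% | 70% | 69% | 74% |
| 42/21, σ 1.0, 20% loss | 87% | 91% | 90% | 93% |
| 21/10.5, σ 1.0, 20% loss | 91% | 92% | 90% | 93% |
| 42/21, σ 0.6 / 1.3, 20% loss (curves cross) | 97% | 93% | 30% | 92% |
| No difference, 10% / 40% loss | 6.1% | 7.2% | 5.0% | 4.8% |

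In the crossing case the 97% goes with an overstated ratio (2.20), so it is not a clean gain. Ranking last covers known non-returners only; patients lost earlier are still left out.

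**Paired data.** The correlation r is assumed. For bivariate normal scores, the unpaired rank statistic has its variance reduced by about 1 − r_s, where r_s = (6/π)·arcsin(r/2). Its true size is therefore about 2·[1 − Φ(1.96/√(1 − r_s))]:
- r = 0.3: r_s = 0.288; 1.96/0.844 = 2.32; size 2.0% (simulated 2.1%).
- r = 0.5: r_s = 0.483; 1.96/0.719 = 2.73; size 0.6% (simulated 0.7%).
- r = 0.7: r_s = 0.683; 1.96/0.563 = 3.48; size 0.05% (simulated 0.1%).

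For a 0.4 SD shift, simulated power at these three correlations is 51–52% for Mann-Whitney, against 66%, 80% and 95% for signed-rank. At 0.8 SD both reach 98% or more.

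**The case against.** **On return to work**, every input is assumed. The cases with clear bias need late or widely spread return: at 42 days and σ 1.3, about 13% of the slow arm is still off work at 6 months, and nothing in the documents supports that. Four of the six postoperative contacts fall within 29 days, so the study looks mainly at early recovery, and with early return the bias nearly vanishes. Visits in the first 3 months are standard care, and a patient who has given a date can be lost later without harm. The yes/no work question can still be compared at each contact with the planned categorical tests. Patient characteristics taken from charts might include work status, although the documents do not list them. All of this stands and limits the size of the problem. It supplies no rule for the weeks variable.

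**On the paired test**, the Mann-Whitney sentence is most naturally read as the partner of the unpaired t-test. No within-group change is a listed endpoint, and the power analysis concerns two independent means. That also stands, and it makes this the minor part.

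**Stronger readings that a reader might infer, and that the documents do not support:**
- *The plan favours one technique.* The direction is not fixed: the ratio can shrink or grow, depending on spread and loss that are not given.
- *Dropping undated patients produces false positives.* Even 10% against 40% loss leaves the type I error near 6%.
- *Patients who do not work bias the result.* The outcome does not apply to them; they reduce the number analysed, with or without the fix.
- *Mann-Whitney on paired data creates false claims or undermines the main comparison.* It is conservative there, and it suits the between-group comparison.
- *Any survival test is better.* Log-rank can be much worse than the planned test when curves cross.

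**Conclusion.** The omission is certain; its effect is not. On a component of a primary endpoint, the plan defines a variable that some patients cannot have, and gives only tests that leave them out. Under the assumptions shown, a true median ratio of 2.0 appears as 1.97 with early return, 1.73 to 1.84 with later return, and 1.55 to 2.20 with unequal spread. The integrals and simulations take loss as unrelated to return, so they do not show what happens if recovery affects response. That could happen here, because at 6 months patients who are doing well are contacted only by phone or email.

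The missing paired test is a wording gap. Applied literally, Mann-Whitney would have a type I error of about 2% down to 0.1% for correlations of 0.3 to 0.7 and would lose power for modest changes. No between-group endpoint is affected by this part.

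Both should be settled before the data are analysed. Neither calls the study design into question.

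**What to change.** **Return to work.**
- Add a work-status field at Visit 1. Define who counts as working before surgery, including how patients already on leave and patients who never stopped work are coded.
- Make sure that the return date is captured alongside the ability question at each contact.
- Add to the Statistical Analysis section:

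> Return to work is analysed as time to event in patients working before surgery, censored at the last contact with a work answer. Kaplan-Meier curves are shown by arm and compared with the Peto-Prentice test. This assumes that loss is unrelated to return. The numbers not working before surgery and lost before return are reported by arm.

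Peto-Prentice is the censored-data form of the planned Mann-Whitney test and holds up if curves cross. If log-rank is preferred, it should be named in advance with that weakness acknowledged.

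**Paired data.** Add:

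> Non-normal within-group comparisons use the Wilcoxon signed-rank test; Mann-Whitney is used only between groups.

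**Cost.** A few sentences, one preoperative field, a date field if the questionnaire lacks one, and slightly more analysis work. No extra patients, visits or procedures are needed. The analysis rests on the loss assumption, and it does not restore the power lost because non-workers do not contribute. In the 42/21-day, σ 1.3 case, Peto-Prentice power falls from 74% to 53% if only 60% work before surgery (an assumed share).
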